3.1.3. Per Protocol Analysis Set

The Week 26 or Week 52 Per Protocol (PP) Analysis Set includes all participants in the FAS excluding participants who committed any major protocol violation, including the violation of key entry criteria.

Participants meeting any of the following criteria will be excluded from the Week 26 or Week 52 PP analysis set:

- 1) did not have on-treatment HIV-1 RNA in the Week 26 or Week 52 analysis window, except when missing is due to discontinuation of study drug for lack of efficacy as in Table 3-1.
(Note: lack of efficacy is defined as having the check-box for Lack of Efficacy marked as the reason for premature study drug discontinuation on the study drug completion eCRF page)
- 2) Received partial or missed oral LEN doses on Day 1 or Day 2.
- 3) Any prior receipt of LEN or a bNAb for HIV-1 treatment (Exclusion criteria 1)
- 4) Have been treated with immunosuppressant therapies or chemotherapeutic agents (eg, corticosteroids, immunoglobulins, and other immune- or cytokine-based therapies) within 4 weeks of study screening or have an anticipated need for such treatment during the study (Exclusion Criteria 3).

Table 3-1. Participants Excluded from Week 26 or Week 52 PP Analysis Set Due to Premature Discontinuation of Study Drug and/or Missing HIV-1 RNA Assessment in Week 26 or Week 52 Analysis Window

Discontinuation from Study Drug prior to or on the Upper Bound of Week 26 Analysis Window		HIV-1 RNA Data on Treatment Available in Week 26 or Week 52 Analysis Window	
		Yes	No
Yes	Due to Lack of Efficacy	+	+
	Due to Other Reasons	+	-
No		+	-

+ = Inclusion of Participants in Week 26 or Week 52 PP analysis set; - = Exclusion of Participants in Week 26 or Week 52 PP analysis set

The PP Analysis Sets are the secondary analysis sets for efficacy analysis.

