3.3. Protocol-Specific Discontinuation Criteria

3.3.1. Criteria for Early Discontinuation for the Individual Participants

3.3.1.1. Criteria for Early Discontinuation for the Individual Participant From Study Intervention

Study interventions will be discontinued in the following instances:

- An AE that would, in the judgment of the investigator, affect assessments of clinical status to a significant degree.
 - Following resolution of the AE, the participant may resume study dosing at the discretion of the investigator.
- Unacceptable toxicity, such as a Grade 3 or higher infusion-related reaction to GS-5423 or GS-2872, per Common Terminology Criteria for Adverse Events (CTCAE) grading scale as defined in Section 7.6, or toxicity that, in the judgment of the investigator, compromises the ability to continue study-specific procedures or is considered not to be in the participant's best interest.
- Lack of efficacy: confirmed VF with emergent resistance to study drugs (refer to Section 6.3.9.2).
- Participant request to discontinue for any reason.
- Participant noncompliance.
- Pregnancy during the study; refer to Appendix 11.3.

- Loss to follow-up.
- Discontinuation of the study by sponsor.

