6.3.9.2.1. Management of Virologic Rebound

Participants who meet the following criteria will be considered to have VR:

- a. At any visit after Day 1, a rebound in HIV-1 RNA \geq 50 copies/mL, which is subsequently confirmed at the following scheduled or unscheduled visit, or
- b. HIV-1 RNA \geq 50 copies/mL at study drug discontinuation

At any visit after Day 1, if the HIV-1 RNA is ≥ 50 copies/mL and < 200 copies/mL, a reflex HIV-1 RNA repeat test will be conducted on stored plasma samples, if available. If the repeat result is < 50 copies/mL, no further action is required. If the repeat result is ≥ 50 copies/mL, participants will be asked to return to the clinic for a scheduled or unscheduled blood draw (2 to 3 weeks after the date of the original test with HIV-1 RNA ≥ 50 copies/mL) for confirmation of VR. If VR is confirmed and HIV-1 RNA is ≥ 50 copies/mL and < 200 copies/mL, the participant will be asked to return to the clinic for a scheduled or unscheduled blood draw (2 to 3 weeks after the date of the confirmatory draw) and the participant should be discussed with the medical monitor. If VR is confirmed and HIV-1 RNA is ≥ 200 copies/mL, the plasma sample from either the first instance or the confirmation visit will be used for HIV-1 capsid and envelope genotypic and phenotypic testing. A plasma sample from the confirmation visit will be the primary sample used for HIV-1 PR, RT, and IN genotypic and phenotypic testing. After a participant's first postbaseline resistance test, additional testing will be conducted on a case-by-case basis. Any participant may be discontinued at investigator's discretion or per local treatment guidelines.

If no resistance is detected from the genotype or phenotype, the participant may remain on study drugs, and the HIV-1 RNA test should be repeated (2 to 3 weeks after the date of confirmed test with HIV-1 RNA ≥ 50 copies/mL). If HIV-1 RNA levels remain ≥ 50 copies/mL, the participant's discontinuation should be discussed with the medical monitor. If resistance to study drug is detected, participants receiving a long-acting study drug regimen will be restarted on their baseline oral ART regimen (or compatible regimen selected by the investigator) and continue on-study follow-up but will not receive additional doses of the study drugs. Investigators who opt to discontinue study drugs for an individual participant must discuss with the medical monitor prior to study drug discontinuation.

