6.1.2. US FDA-Defined Snapshot Algorithm

The analysis window at Week 26 is defined as from Study Day 176 to Study Day 224, inclusive for treatment group 1 and Study Day 134 to Study Day 224, inclusive for treatment group 3. All HIV-1 RNA data collected on-treatment during the randomized phase will be used in the US FDA-defined snapshot algorithm. Virologic outcome will be defined as the following categories:

- **HIV-1 RNA < 50 copies/mL:** this includes participants who have the last available on-treatment HIV-1 RNA < 50 copies/mL in the Week 26 analysis window
- **HIV-1 RNA ≥ 50 copies/mL:** this includes participants
 - a) Who have the last available on-treatment HIV-1 RNA ≥ 50 copies/mL in the Week 26 analysis window, or
 - b) Who do not have on-treatment HIV-1 RNA data in the Week 26 analysis window and
 - Who discontinue study drug prior to or in the Week 26 analysis window due to lack of efficacy, or
 - Who discontinue study drug prior to or in the Week 26 analysis window due to AE or death and have the last available on-treatment HIV-1 RNA ≥ 50 copies/mL, or
 - Who discontinue study drug prior to or in the Week 26 analysis window due to reasons other than AE, death, or lack of efficacy and have the last available on-treatment HIV-1 RNA ≥ 50 copies/mL.

- **No Virologic Data in the Week 26 Window:** this includes participants who do not have on-treatment HIV-1 RNA data in the Week 26 analysis window because of the following:
 - Discontinuation of study drug prior to or in the Week 26 analysis window due to AE or death and the last available on-treatment HIV-1 RNA < 50 copies/mL, or
 - Discontinuation of study drug prior to or in the Week 26 analysis window due to reasons other than AE, death, or lack of efficacy and the last available on-treatment HIV-1 RNA < 50 copies/mL or,
 - Missing data during the window but on study drug.

The flowchart of the US FDA-defined snapshot algorithm is provided in Appendix 2.

The Week 26 virologic outcomes for the US FDA-defined snapshot algorithm will be listed.

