6.1.3. Analysis of the Primary Efficacy Endpoint

The Primary analysis of the proportion of participants with HIV-1 RNA ≥ 50 copies/mL as determined by the US FDA-defined snapshot algorithm at Week 26 will be based on the FAS. The 95% CI of the proportion of participants with HIV-1 RNA ≥ 50 copies/mL for each treatment group will be provided using the Clopper-Pearson Exact method. The point estimate of treatment difference in the percentage of participants with HIV-1 RNA ≥ 50 copies/mL and the associated 2-sided 95% CI will be constructed based on an unconditional exact method using 2 inverted 1-sided tests {Chan 1999}.

The Fisher's exact test will also be used to compare the percentages of participants between treatment groups. A secondary analysis based on the Week 26 PP analysis set will also be performed.

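### The Per Protocol sets exclude some participants whom the snapshot counts as failures: those with no on-treatment HIV-1 RNA in the window, a last value of 50 copies/mL or more, and a stop reason other than lack of efficacy

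*SAP*

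**What the plan says.** The FAS is the primary efficacy set (SAP 3.1.2) and the PP sets are secondary (SAP 3.1.3). PP criterion 1 removes participants with no on-treatment HIV-1 RNA in the Week 26 or Week 52 window, "except when missing is due to discontinuation of study drug for lack of efficacy as in Table 3-1". A note adds that "lack of efficacy is defined as having the check-box for Lack of Efficacy marked as the reason for premature study drug discontinuation". Table 3-1 divides premature stops into lack of efficacy and "Due to Other Reasons". With no window data, the first is kept and the second is excluded, whatever the last viral load.

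The snapshot (SAP 6.1.2) has three routes to HIV-1 RNA ≥ 50 copies/mL without window data. One is a stop for lack of efficacy. The other two are a stop "due to AE or death and have the last available on-treatment HIV-1 RNA ≥ 50 copies/mL" and a stop "due to reasons other than AE, death, or lack of efficacy and have the last available on-treatment HIV-1 RNA ≥ 50 copies/mL".

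Both sets serve the same endpoint. For Week 26, SAP 6.1.3 states: "A secondary analysis based on the Week 26 PP analysis set will also be performed". SAP 6.2.2.1 does the same for Week 52.

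**The concern.** The snapshot uses the last on-treatment viral load to recognise a failure when the window is empty. The PP rule uses a tick-box. Where the two disagree, a participant with known viraemia is a failure in the FAS and is missing from both numerator and denominator in the PP analysis. The SAP keeps lack-of-efficacy stops without window data, so it evidently means virologic failures of this kind to stay. No section restores the others or says why they should go.

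The stake is how the PP result reads. With so few events, a PP failure rate below the FAS rate could be taken as reassurance when part of the gap comes from removed failures.

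**Working it through.** **1. Matching the rules.** All rows are FAS participants with no on-treatment HIV-1 RNA in the window.

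| Situation | Snapshot class (SAP 6.1.2) | PP set (SAP 3.1.3) |
|---|---|---|
| Stopped, Lack of Efficacy ticked | ≥ 50 | kept |
| Stopped for AE or death, last value ≥ 50 | ≥ 50 | excluded |
| Stopped for another reason, last value ≥ 50 | ≥ 50 | excluded |
| Stopped for AE, death or another reason, last value < 50 | no virologic data | excluded |
| On study drug, value missing | no virologic data | excluded |

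Rows 2 and 3 are the mismatch. Anyone with on-treatment RNA in the window stays in the PP set whatever the stop reason.

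**2. Can rows 2 and 3 occur?** Protocol 3.3.1.1 gives the stopping criterion as "Lack of efficacy: confirmed VF with emergent resistance to study drugs" and lists participant request separately. Protocol 6.3.9.2.1 adds: "Any participant may be discontinued at investigator's discretion or per local treatment guidelines". A stop after rebound without detected resistance could therefore be recorded under another reason. In Group 1, on-treatment data end at the earlier of ART restart and 196 days after the last complete dose (SAP section 6).

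- Rebound at Week 12 (Day 84) or Week 38 (Day 266), confirmed up to 21 days later, gives 84 + 21 = Day 105 or 266 + 21 = Day 287. The windows open on Day 176 and Day 358. These are confirmation dates, not ART restart dates, but they leave time for a restart before the window.
- Protocol 5.3 requires suppression at the preceding visit before Week 26 dosing. A participant not re-dosed has on-treatment data only to Day 1 + 196 = Day 197, so none from Day 358.

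**3. Direction.** With x failures among n, dropping k failures gives (x − k)/(n − k), which is below x/n whenever x < n. Dropping m participants whose last value was < 50 (or who have no value) gives x/(n − m), which is above x/n. For example, 3/50 = 6.0% becomes 3/48 = 6.3% with m = 2. The net effect depends on both k and m.

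**4. The plan's own figure.** SAP 1.3 says the exact 95% CI for the difference excludes 0 from 8/50 against 0/25, and from 12/50 against 1/25. An exact unconditional test with the score statistic at one-sided 0.025 reproduces both. Against 0/25, p = 0.0403 for 7/50 and 0.0239 for 8/50. Against 1/25, p = 0.0403 for 11/50 and 0.0239 for 12/50. At the first threshold, one excluded failure gives 7/49 against 0/25, p = 0.0417, and the interval (−1.1 to 27.3 points) includes 0.

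**5. Illustration with the reported counts.** Protocol 1.4.1.2 reports 1 failure at Week 26 and 3 at Week 52 on the long-acting regimen, and none on baseline regimen. Assumed: 50 analysed in Group 1 and k as shown. Intervals are Clopper-Pearson 95%.

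| k | Week 26 | Week 52 |
|---|---|---|
| 0 | 1/50 = 2.0% (0.1 to 10.6) | 3/50 = 6.0% (1.3 to 16.5) |
| 1 | 0/49 = 0% (0 to 7.3) | 2/49 = 4.1% (0.5 to 14.0) |
| 2 | – | 1/48 = 2.1% (0.1 to 11.1) |
| 3 | – | 0/47 = 0% (0 to 7.5) |

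One exclusion at Week 52 cuts the estimate by (6.0 − 4.1)/6.0, about a third. Against an assumed 0/25, the interval for the difference includes 0 in every cell.

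**The case against.** Four points have force.

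- **Criterion 1 acts on missing data, not on outcome.** A reader might infer that participants are removed because they failed, or that the PP analysis is biased downward overall. The documents do not support either. The rule also removes participants whose last value was < 50, which pushes the rate up.
- **The tick-box route is plausible but not shown.** The protocol's resistance condition governs stopping treatment, and the SAP's check-box does not require it. Protocol 6.3.9.2 treats rebound as virologic failure, so an investigator might well tick Lack of Efficacy. Repeat draws and resistance testing can also keep a participant on study drug for longer.
- **The reported failures may not be affected.** Nothing shows that any of the 1 or 3 was of this type. Those counts are also far below the 8 needed for the interval to exclude 0, so the reversal at the design threshold is not a statement about this trial's data.
- **There are safeguards.** The FAS is primary, the study is not powered for comparison, SAP 3.1 requires exclusions and reasons by group with a listing, and SAP 6.3.2.1 analyses all collected data by visit.

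These points limit the size of the problem but do not remove the mismatch. The exclusion summary is not required to say which excluded participants were snapshot failures; a reader would have to cross-match listings.

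**Conclusion.** The point holds in a narrow form. In both PP sets, criterion 1 and Table 3-1 exclude a participant whom the snapshot counts as HIV-1 RNA ≥ 50 when three conditions meet: no on-treatment value in the window, a last on-treatment value ≥ 50, and a stop not ticked as lack of efficacy. Each such case lowers the PP failure rate; the net effect of criterion 1 is unknown.

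The illustrated size, 6.0% to 4.1% at Week 52 or 2.0% to 0% at Week 26, assumes 50 analysed and exactly one case. The number of cases is not stated and may be zero. A reader might go further and conclude that every failure without the tick is dropped, or that the primary result is compromised. Neither follows: participants with window data stay in, and the FAS analysis is untouched. This is worth correcting in a secondary analysis because the SAP's own treatment of lack-of-efficacy stops shows the intent.

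**What to change.** In SAP 3.1.3, amend criterion 1 and the Table 3-1 cell for other stop reasons with no window data. Retain participants whose last available on-treatment HIV-1 RNA is ≥ 50 copies/mL, and exclude those whose last value is < 50. State that criteria 2 to 4 and any other major protocol violation take precedence, so that a snapshot failure excluded on those grounds stays excluded.

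SAP 2.2 describes the Week 26 primary analysis as already done, and Protocol 1.4.1.2 reports Week 52 results. If the PP analyses have been run, leave them as specified. Report by arm how many snapshot failures criterion 1 removed, and give the PP estimate with them retained as a labelled sensitivity analysis.

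The cost is one clause, one table cell and a line of programming, or one extra count and table if done afterwards. The PP failure rate may look slightly less favourable. Retention without window data would depend on the last viral load, as it in effect already does for lack-of-efficacy stops.

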4.3. Exclusion Criteria

Participants who meet any of the following exclusion criteria are not eligible to be enrolled in this study:

- 1) Any prior receipt of LEN or a bNAb for HIV-1 treatment.
- 2) Receipt of long-acting injectable ARV within 6 months of Screening Visit 2.

- 3) Have been treated with immunosuppressant therapies or chemotherapeutic agents (eg, corticosteroids, immunoglobulins, and other immune- or cytokine-based therapies) within 4 weeks of Screening Visit 2 (with the exception of a single short course of corticosteroids lasting ≤ 7 days) or have a comorbid condition with an anticipated need ongoing immunosuppressive treatment during the study.
- 4) Pregnant participants assigned female at birth or plans to become pregnant during the course of the study.
- 5) Lactating participants assigned female at birth.
- 6) Participation in any other clinical study, including observational studies, without prior approval from the sponsor.
- 7) Clinically significant abnormal electrocardiogram (ECG) at the Screening Visit 2.
- 8) Hepatitis C virus (HCV) antibody positive and HCV RNA detectable.
- 9) Chronic hepatitis B virus (HBV) infection, as determined by either: positive HBV surface antigen and negative HBV surface antibody, regardless of HBV core antibody status, at the screening visit, or positive HBV core antibody, negative HBV surface antibody regardless of HBV surface antigen status, at Screening Visit 2.
- 10) Active, serious infections (other than HIV-1 infection) requiring systemic antibiotic or antifungal therapy within 30 days prior to Screening Visit 2.
- 11) Have poor venous access that would limit phlebotomy or IV infusion of study drugs.
- 12) Have a history of any of the following:
 - A) Opportunistic infection or illness indicative of Stage 3 HIV disease.
 - B) Known hypersensitivity to the study drug, the metabolites, or formulation excipient.
 - C) Malignancy within the past 5 years (prior to screening) or ongoing malignancy, other than basal cell carcinoma, or resected, noninvasive cutaneous squamous carcinoma.
 - D) Substance abuse or a psychiatric or medical condition that could, in the opinion of the investigator, compromise the participant's ability to participate in the study.

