Premedications will not be routinely administered prior to study drug administration. Participants who experience mild-moderate infusion-related reactions may be premedicated for subsequent infusions if determined necessary by the investigator. Premedication may consist of one or more of the following medications: diphenhydramine 25 mg (oral), ibuprofen 400 to 600 mg (oral), acetaminophen 500 to 650 mg (oral), prednisone 20 to 40 mg (oral) or equivalent alternative steroid.

The exact time of study drug administrations must be recorded in the source document. For additional information, refer to the study Pharmacy Manual.

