6.2. Screening, Participant Enrollment, and Treatment Assignment

Due to the extended laboratory processing time of the GS-5423 and GS-2872 proviral DNA phenotype testing (up to approximately 10 weeks), the screening visit will be performed in 2 parts ([Table 1](#) and [Table 2](#)). Participants meeting all of the inclusion criteria and none of the exclusion criteria will return to the clinic within 28 days after the Screening Visit 2 for the Day 1 visit. It is the responsibility of the investigator to ensure that participants are eligible to participate in the study prior to enrollment and continue to remain eligible throughout the study. The medical monitor may be contacted regarding any questions related to eligibility.

If the screening window is exceeded in an otherwise eligible participant, the participant is allowed to rescreen (Screening Visit 2) 1 time after approval from the sponsor. Once a participant has started the rescreening process, a new screening window (28 days) will begin, during which time screening procedures will be repeated.

Entry into screening does not guarantee enrollment into the study. In order to manage the total study enrollment, Gilead, at its sole discretion, may suspend screening and/or enrollment at any site or study wide at any time.

Participants must continue to take their baseline oral ART until completion of study drug administration at the Day 1 visit (Treatment Group 1) or Week 52 visit (Treatment Group 3). Once the ICF has been obtained, all screening and eligibility tests and assessments have been assessed, and study eligibility has been confirmed, participants will be randomized to receive study drug on Day 1. Participants will receive the study drugs as described in Section 5.3.

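### SAP Per Protocol item 4 cites protocol Exclusion Criterion 3 but omits its short-course steroid exception and broadens its other limits

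*SAP*

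**What the plan says.** SAP 3.1.3 first gives the purpose of the PP sets: the FAS "excluding participants who committed any major protocol violation, including the violation of key entry criteria". It then lists four specific rules under a mandatory lead-in: "Participants meeting any of the following criteria will be excluded from the Week 26 or Week 52 PP analysis set". Item 4 covers immunosuppressant or chemotherapeutic treatment, with corticosteroids as a named example ("eg, corticosteroids, immunoglobulins, and other immune- or cytokine-based therapies) within 4 weeks of study screening"), and sets its limits as "within 4 weeks of study screening or have an anticipated need for such treatment during the study". The item closes by citing Exclusion Criterion 3.

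Criterion 3 in protocol 4.3 covers the same classes of agent but sets the period as "within 4 weeks of Screening Visit 2" and carries an exemption: "with the exception of a single short course of corticosteroids lasting ≤ 7 days". Its second limb concerns a comorbid condition for which continuing immunosuppression is expected.

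The PP sets are secondary. They support the Week 26 primary endpoint (SAP 6.1.3), the snapshot secondary endpoints (6.2.2.1 and 6.2.2.2) and the CD4 analysis (6.2.2.3). The protocol specifies only the FAS for efficacy (8.3.1.1, 8.5).

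**The concern.** A PP set is meant to show whether the result holds among participants who followed the protocol. If its exclusion rule is broader than the eligibility criterion it cites, it removes people who did follow the protocol.

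The text also leaves two programmers free to build different PP sets, one from the sentence in item 4 and one from the cited criterion. The outputs could then disagree. SAP 3.1 requires a tabulated reason for every exclusion from an analysis set, and SAP 4.5 separately tabulates unmet eligibility criteria. One participant could appear as a Criterion 3 exclusion in the first output and have no eligibility deviation in the second. With so few virologic failures in this trial, membership of the PP set should not rest on a transcription difference.

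**Working it through.** No figure in the plan depends on this rule, so the check is a comparison of texts followed by an illustration of size.

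**Step 1: the two rules side by side**

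| Element | Protocol 4.3, Criterion 3 | SAP 3.1.3, item 4 |
|---|---|---|
| Short steroid course | Exempt if single and 7 days or less | No exemption; corticosteroids named as covered |
| Start of the 4 weeks | Screening Visit 2 | Screening in general, visit not stated |
| Anticipated need | Comorbid condition, continuing immunosuppression | Any anticipated need for the listed treatments |

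**Step 2: does the visit matter?** Protocol 6.2 splits screening in two because of the time needed for "GS-5423 and GS-2872 proviral DNA phenotype testing (up to approximately 10 weeks" of laboratory processing. Table 1, footnote a, says Visit 2 follows review of those results. The visits can therefore be well over 4 weeks apart. If screening is read as Visit 1, a participant treated just before Visit 1 but more than 4 weeks before Visit 2 is compliant and is removed. A participant treated just before Visit 2 breaches the criterion but is not caught by the first limb of item 4, and would have to be caught by the general sentence on major violations.

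**Step 3: is the difference restored or explained elsewhere?** The key eligibility list in the SAP does not mention Criterion 3, and nothing presents item 4 as deliberately stricter. The SAP rests on Amendment 3 and the protocol supplied is Amendment 4. The Amendment 4 log lists no change to Section 4.3, and no log entry mentions the steroid exemption. The move to Screening Visit 2 in Section 4.3 is logged under Amendment 2, before the version the SAP used. The log is high-level, so a version difference is unlikely but not excluded.

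**Step 4: illustration of size.** Inputs: 50 planned in Group 1 (SAP 1.3); 1 Group 1 failure at Week 26 and 3 at Week 52, none in Group 3 (protocol 1.4.1.2). Assumption: 1 to 5 Group 1 participants removed by item 4 and by nothing else. Rate = failures / remaining participants, with Clopper-Pearson 95% intervals.

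| | None removed | 1 removed, not a failure | 1 removed, a failure | 5 removed, no failure | 5 removed, one a failure |
|---|---|---|---|---|---|
| Week 26 | 1/50 = 2.0% (0.05 to 10.65) | 1/49 = 2.0% (0.05 to 10.85) | 0/49 = 0% (0 to 7.25) | 1/45 = 2.2% (0.06 to 11.77) | 0/45 = 0% (0 to 7.87) |
| Week 52 | 3/50 = 6.0% (1.25 to 16.55) | 3/49 = 6.1% (1.28 to 16.87) | 2/49 = 4.1% (0.50 to 13.98) | 3/45 = 6.7% (1.40 to 18.27) | 2/45 = 4.4% (0.54 to 15.15) |

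Group 3 stays at 0% whoever is removed.

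**The case against.** Item 4 cites Criterion 3 and sits under a sentence about violations. A careful programmer could follow the citation, apply the protocol criterion and remove nobody wrongly. On that view the text is loose rather than wrong, and a sponsor may in any case make a PP set stricter than eligibility. Part of this stands: the error may have no effect in practice. But the lead-in makes each listed item decisive, the item names corticosteroids without exemption, and no stricter intent is stated.

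A reader might infer a route to bias through premedication. Protocol 5.3.1 allows "prednisone 20 to 40 mg (oral) or equivalent alternative steroid" among other options, and only Group 1 receives infusions before Week 52. The documents do not support this. Both limbs of item 4 are judged at entry: treatment around screening, or need anticipated then. Premedication is not routine; it is allowed for later infusions after a mild to moderate reaction on study, which was not anticipated at entry. In the Phase 1b study one mild infusion reaction was reported in the primary cohort, resolving untreated, and none in the pilot cohort (protocol 1.2.4).

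A reader might also infer that the PP comparison becomes biased. What remains is exclusion on a characteristic fixed before randomization, applied to both arms. That shrinks the set but does not by itself bias the comparison.

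Finally, the falls from 2% to 0% and from 6% to about 4% are hypothetical. They require a failing participant to be one of those removed. The protocol describes the three participants with failure by weight and exposure and says nothing of steroid use.

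**Conclusion.** Wrong as written, minor. Item 4 departs from its stated source in three respects, and its literal application would remove protocol-compliant participants from the Week 26 and Week 52 PP sets, against the section's own purpose.

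The effect is confined to secondary analyses in a trial not powered for comparison; the FAS primary analysis is untouched. The size is unknown, because the documents do not say whether anyone enrolled had a short steroid course or fell between the two screening anchors. If only non-failures are removed, the Group 1 rate moves by 0.7 percentage points at most for up to five removals (6.0% to 6.7% at Week 52). The illustration rests on planned rather than actual denominators. The conclusion also assumes that Criterion 3 read the same in Amendment 3 as in Amendment 4, which the amendment log supports but does not prove.

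**What to change.** Replace the text of item 4 with protocol Exclusion Criterion 3 verbatim: the exemption for one short corticosteroid course, the Screening Visit 2 anchor, and the comorbid-condition limb. If a stricter PP rule was intended, say so, give the reason, and drop the implication that it reproduces the criterion. In either case report, by arm, how many participants item 4 removes.

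The cost is one sentence and one count. Timing needs care. Protocol 1.4.1.2 already reports Week 52 failures, and SAP 1 says the plan is finalized before the Week 52 data are. The change should therefore be entered in the SAP revision table (Section 12) as a correction to existing protocol wording, made without reference to results. If it changes who is in a PP set, show the PP results under both wordings; if it changes nobody, one statement to that effect closes the matter.
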